3.2.2 Secondary Efficacy Endpoints

- 1. The 7-day average of maximum daily pain NRS scores prior to Visits 1, 3, 4, 5, and 6 will be used to evaluate the number (%) of subjects with:
 - Changes in pain categories from Visit 1 (Day 1) to Visits 3 (Day 29), 4 (Day 57), 5 (Day 85) and 6 (Day 113) (See Section 6.2.2.2 *Pain Categories*)
 - Improvement of 30% from Visit 1 (Day 1) to Visits 3 (Day 29), 4 (Day 57), 5 (Day 85) and 6 (Day 113)
 - Improvement of 50% from Visit 1 (Day 1) to Visits 3 (Day 29), 4 (Day 57), 5 (Day 85) and 6 (Day 113)
 - Improvement of 75% from Visit 1 (Day 1) to Visits 3 (Day 29), 4 (Day 57), 5 (Day 85) and 6 (Day 113)

- Improvement of 100% from Visit 1 (Day 1) to Visits 3 (Day 29), 4 (Day 57), 5 (Day 85) and 6 (Day 113)
- 2. Trends in active musculoskeletal disease activity over the duration of the treatment period (i.e. Visit 1 (Day 1) through Visit 5 (Day 85)) will be evaluated longitudinally using multiple indices:
 - Physician assessed tender joint count
 - Physician assessed swollen joint count
 - Presence or absence of arthritis on the SELENA SLEDAI
 - Musculoskeletal domain of the BILAG 2004
- 3. Persistence of trends in musculoskeletal disease activity after stopping treatment will be evaluated at Visit 6 (Day 113).
- 4. Trends in overall SLE disease activity over the duration of the treatment period (i.e. Visit 1 (Day 1) through Visit 5 (Day 85)) will be evaluated longitudinally using multiple indices:
 - SLE Responder Index, where a responder is defined as having all of the following:
 - $\circ \geq 4$ point reduction in SELENA-SLEDAI score,
 - no new BILAG A or no more than 1 new BILAG B domain score, and
 - no deterioration from baseline in the Physician's Global Assessment defined as an increase of ≥0.3 points.
 - SELENA SLEDAI score
 - BILAG 2004 score
 - Physician's Global Assessment
- 5. Persistence of trends in overall SLE disease activity after stopping treatment will be evaluated at Visit 6 (Day 113).
- 6. Trends in patient-reported outcomes over the duration of the treatment period (i.e. Visit 1 (Day 1) through Visit 5 (Day 85)) will be evaluated longitudinally using multiple indices:
 - Lupus Activity Patient Global Assessment
 - PROMIS-29 Short Form
 - PROMIS Item Bank v2.0 Cognitive Function
- 7. Treatment Satisfaction Survey
- 8. Persistence of trends in patient-reported outcomes after stopping treatment will be evaluated at Visit 6 (Day 113).

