3.2.3 Safety Endpoints

Safety will be evaluated by describing incidence of treatment-emergent adverse events (TEAEs) from Visit 1 (Day 1) through 6. TEAEs will be identified by monitoring subject-reported AEs, vital signs, medical history, physical exams, blood and urine safety tests, 12-lead electrocardiograms, and the ARCI-M. Analyses on the following specific events are planned.

- 1. Any Grade 3 or higher AE or SAE that, in the opinion of the blinded site investigator, is at least possibly related to study product. Unless noted otherwise, grading is defined by the National Cancer Institute (NCI) Common Terminology Criteria for Adverse Events (CTCAE) system version 4.0.
- 2. QTc prolongation > 500 msec total duration and > 60 msec from Visit 1 (Day 1) QTc interval prior to study drug administration
- 3. Mild/moderate and severe disease flares by SELENA SLEDAI Flare Index
- 4. BILAG 2004 disease flares, defined as one new BILAG A or two new BILAG B scores
- 5. Aspartate aminotransferase (AST) or alanine aminotransferase (ALT) \ge 3 x upper limit of normal and total bilirubin > 1.5 x the upper limit of normal (confirmed on repeat testing)
- 6. Tolerability, assessed by incidence of discontinuation of study product due to TEAEs at least possibly related to study product from Visits 1 (Day 1) through 5 (Day 85)
- 7. Psychotropic activity, assessed using the ARCI-M

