6.1.5.1 SELENA SLEDAI (28 day assessment)

The SELENA SLEDAI is a validated measure of global disease activity in SLE and was modified from the original SLEDAI for the SELENA clinical trial in 1997. The original SLEDAI was developed in 1992; it includes both subjective reports from patients and objective findings from physicians and laboratory data [111]. The SELENA SLEDAI modification of the original SLEDAI changed some of the item definitions in order to clarify attribution and change in disease activity. These included changes to definitions of seizure activity, strokes, serositis, visual disturbances and proteinuria [109, 112].

The SELENA SLEDAI is a one page assessment that contains 24 items covering 9 organs systems and items are scored as either present or absent. Each item is assigned a weighted score. Two systems can score a maximum of 8 points each, 2 systems can score a maximum of 4 points each, 3 systems can score a maximum of 2 points each, and 2 systems can score a maximum of 1 point each. Scores range from 0–105 points. A score of 6 is considered clinically important and may affect the decision to treat. The original SLEDAI captured disease activity within the 10 days prior to assessment; however, this time period was extended to include the previous 30 days [113, 114].

The SLEDAI does not record improving or worsening, and does not include severity within an organ system. The sensitivity to change is less for the SLEDAI than other commonly used outcome measures in SLE [115].

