6.1.5.2 BILAG 2004

The purpose of the BILAG is to assess organ-specific SLE activity based upon the "intent-totreat" premise. The updated version (BILAG 2004) was published in 2005 and is a validated measure of disease activity [110]. BILAG 2004 assesses 97 clinical signs, symptoms and laboratory parameters important in SLE across nine organ systems. Each symptom is scored with respect to severity over the previous 28 days (0 = not present, 1 = improving, 2 = same, 3 = worse, and 4 = new). The BILAG provides a more sensitive measure of change than the SLEDAI [115].

As above, each question is recorded as 0, 1, 2, 3, or 4. The BILAG 2004 scoring algorithm categorizes disease activity into 5 different levels from A–E. Grade A represents very active disease likely necessitating immunosuppressive drugs and/or a prednisolone (or equivalent)

dose of > 20 mg daily or high-dose anti-coagulation. Grade B represents moderate disease activity prompting consideration of a lower dose of corticosteroids, topical steroids, topical immunosuppressive drugs, anti-malarial drugs, or nonsteroidal anti-inflammatory drugs. Grade C indicates mild stable disease, while grade D implies no disease activity but the system had previously been affected. Grade E indicates no current or previous disease activity.

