6.1.5.3 Flare Definitions

Disease flares will be defined using SELENA SLEDAI Flare Index and BILAG 2004 assessments. See Section 3.2.3, *Safety Endpoints* and Section 7.4.1, *Grading Criteria* for definitions and severity grading requirements.

The SELENA SLEDAI Flare Index categorizes disease flares as mild/moderate or severe, based on the highest categories of clinical features recorded or by treatment recommendations by the physician.

SELENA SLEDAI and BILAG 2004 disease flares will be identified centrally at the DAIT-SACCC.

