6.2.2 Secondary Efficacy Variables

For any individual subject, the same physician should, if possible, assess the 66/68 joint count, physician-reported components of the SELENA SLEDAI and BILAG 2004 score, and the Physician's Global Assessment. The SLE Responder Index, SELENA SLEDAI score, and BILAG 2004 domain scores will all be calculated centrally at the DAIT-SACCC.

6.2.2.1 **Response Categories**

Improvement will be computed at the % change in the 7-day average of maximum daily pain NRS scores from Visits 1(Day 1) to Visits 3 (Day 29), 4 (Day 57), 5 (Day 85), and 6 (Day 113). Categories for 30%, 50%, 75% and 100% improvement will be evaluated.

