7.4 Grading and Attribution of Adverse Events

7.4.1 Grading Criteria

The study site will grade the severity of adverse events experienced by the study subjects according to the criteria set forth in the National Cancer Institute's Common Terminology Criteria for Adverse Events (CTCAE) version 4. This document (referred to herein as the NCI-CTCAE manual) provides a common language to describe levels of severity, to analyze and interpret data, and to articulate the clinical significance of all adverse events. The NCI-CTCAE has been reviewed by the Protocol Chairs and has been deemed appropriate for the subject population to be studied in this protocol.

Adverse events will be graded on a scale from 1 to 5 according to the following standards in the NCI-CTCAE manual:

- Grade 1 = mild adverse event.
- Grade 2 = moderate adverse event.
- Grade 3 = severe and undesirable adverse event.
- Grade 4 = life-threatening or disabling adverse event.
- Grade 5 = death.

For grading an abnormal value or result of a clinical or laboratory evaluation (including, but not limited to, a radiograph, an ultrasound, an electrocardiogram etc.), a treatment-emergent adverse event is defined as an increase in grade from baseline or from the last post-baseline value that doesn't meet grading criteria (i.e. Grade 0, normal). Similarly, changes from screening to baseline will also be recorded as adverse events, but these are not treatment-emergent. If a specific event or result from a given clinical or laboratory evaluation is not included in the NCI-CTCAE manual, then an abnormal result would be considered an adverse event if changes in therapy or monitoring are implemented as a result of the event/result. Grade 2 or higher AEs will be reported on the appropriate AE electronic case report (AE eCRF) for this study.

In addition, for this study, BILAG 2004 disease flares will be graded as follows:

- Mild SLE flare (Grade 1): New BILAG 2004 grade C in one or more organ systems
- Moderate SLE flare (Grade 2): New BILAG 2004 grade B in one or more organ systems
- Severe SLE flare (Grade 3): New BILAG 2004 grade A in one organ system
- Life-threatening or disabling SLE flare (Grade 4): A life-threatening or disabling new BILAG 2004 grade A

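### The BILAG component of the SLE Responder Index is joined by *or*, so a subject can meet the protocol's BILAG flare endpoint and still pass that component at the same visit

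*Protocol*

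**What the plan says.** Section 3.2.2 (secondary endpoint 4) introduces the index as "SLE Responder Index, where a responder is defined as having all of the following". Three components follow: a SELENA-SLEDAI fall of at least 4 points, the BILAG component "no new BILAG A or no more than 1 new BILAG B domain score", and no rise of 0.3 or more in the Physician's Global Assessment. The synopsis uses the same words for the BILAG component.

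Section 3.2.3 (safety endpoint 4) counts "BILAG 2004 disease flares, defined as one new BILAG A or two new BILAG B scores". Section 7.4.1 grades flares for adverse event reporting and places "New BILAG 2004 grade A in one organ system" at Grade 3, severe.

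Section 6.2.2.4 describes the index only as a composite with a literature citation and does not restate the BILAG component. Both quantities come from the same centre: section 6.1.5.3 states that "SELENA SLEDAI and BILAG 2004 disease flares will be identified centrally", and section 6.2.2 that "The SLE Responder Index, SELENA SLEDAI score, and BILAG 2004 domain scores will all be calculated centrally". No section gives the component with *and*.

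**The concern.** The three components must all be met, so the *or* acts only inside the BILAG component. There it joins two separate negative conditions, and satisfying either one is enough. A subject with a new A in one domain and no new B satisfies the second condition. A subject with three new Bs and no new A satisfies the first. Section 3.2.3 counts both as flares.

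If the rule were programmed as written, a subject could be counted as an SLE responder at the visit where the same centre records a BILAG flare. The BILAG component would no longer screen out worsening in one organ system while another improves. The SLEDAI cannot fully take over that task, because section 6.1.5.1 says: "The SLEDAI does not record improving or worsening, and does not include severity within an organ system". Secondary analyses are exploratory, but section 8.3 gives dose selection and the powering of later pivotal studies among their purposes, so a distorted responder rate would have some use made of it.

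**Working it through.** The protocol states no figure to reproduce; the check is logical. Let A be the number of domains with a new BILAG A and B the number with a new BILAG B, at one visit.

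**Rules**

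- Flare endpoint (3.2.3): A ≥ 1 or B ≥ 2.
- Component as written (3.2.2 and synopsis): A = 0 or B ≤ 1.
- Component with *and*: A = 0 and B ≤ 1.

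The negation of the flare rule is A = 0 and B ≤ 1, which is the *and* version. The negation of the written component is A ≥ 1 and B ≥ 2, so that is the only way to fail it.

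**Six grouped cells**

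| A | B | Flare (3.2.3) | Passes as written | Passes with *and* |
|---|---|---|---|---|
| 0 | 0 | no | yes | yes |
| 0 | 1 | no | yes | yes |
| 0 | ≥ 2 | yes | yes | no |
| ≥ 1 | 0 | yes | yes | no |
| ≥ 1 | 1 | yes | yes | no |
| ≥ 1 | ≥ 2 | yes | no | no |

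Four cells are flares. Three of the four pass as written; none pass with *and*.

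**Ungrouped counts.** Section 6.1.5.2 says "BILAG 2004 assesses 97 clinical signs, symptoms and laboratory parameters important in SLE across nine organ systems", so A + B ≤ 9.

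- Possible pairs: 10 + 9 + … + 1 = 55.
- Not flares: (0,0) and (0,1), leaving 55 − 2 = 53 flare pairs.
- Flare pairs that pass as written: A = 0 with B = 2 to 9 gives 8; B = 0 with A = 1 to 9 gives 9; B = 1 with A = 1 to 8 gives 8. Total 8 + 9 + 8 = 25.
- Flare pairs that pass with *and*: 0. That version is the exact complement of the flare rule in all 55 pairs.

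The fraction depends on the grouping (3 of 4, or 25 of 53). Neither is a patient frequency.

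**Weight of one subject.** With 25 per arm (section 3.1, Table 1), 1/25 = 4.0 percentage points. With the 22 per arm considered in section 8.1, 1/22 = 4.5 points. This is the weight of any single reclassified subject in a binary endpoint, not an estimate of bias.

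**Would such subjects be in the data?** BILAG A at Screening is an exclusion (4.2), so an A on treatment would ordinarily be new. Section 5.8.1 exempts a musculoskeletal BILAG A from the BILAG criterion for stopping study treatment. Subjects who stop are asked, where possible, to complete all visits and assessments (5.8.1.1). Efficacy analyses use all treated randomized subjects regardless of compliance (8.2.1), and the exclusion of data after stopping treatment is stated for the pain NRS only (8.3.2.1). Nothing in the protocol therefore removes a flaring subject from the responder analysis.

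**The case against.** - **The intent is obvious and the algorithm is not shown.** The index is presented as an existing, cited composite, scoring is central, and an analysis plan will follow. This is probably a drafting slip, and the program may already use *and*. That stands, and it limits confidence to the wording. But the phrase repeats the negative, so it does not read naturally as neither/nor, and it appears identically in both places. This is a stated definition, not a detail left for later.

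- **The other two components protect the index.** A misclassified responder needs a SELENA-SLEDAI fall of at least 4 and no Physician's Global Assessment rise of 0.3 or more at the same visit as the new A or the multiple new Bs. The global assessment is completed once the visit's information is available (6.2.2.4), so it would catch some of these subjects. That stands as a reason to expect few cases. It does not make the component right: SLEDAI items are scored present or absent, and the global assessment is a separate judgement.

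- **The *and* version still admits something the protocol calls a flare.** Section 7.4.1 grades a single new B as a moderate, Grade 2 flare. On that grading five of the six cells are flares; the written rule passes four and *and* passes one, namely no new A with one new B. This is correct, so the claim is tied to the flare endpoint in 3.2.3. Tolerating one new B is an explicit feature of the index and is not in dispute.

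- **The consequence is small.** The index is one of several secondary measures, p-values are descriptive (8.8), and flares are reported separately. All of that stands.

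**Conclusion.** The concern holds. As written, the BILAG component passes three of the four grouped patterns that section 3.2.3 defines as a flare, including a new A alone, which section 7.4.1 grades as severe. With *and* it passes none.

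This rests on the literal reading of the sentence and on comparing the two rules at the same visit. How many subjects would be misclassified, and so the size of any inflation of responder rates, cannot be determined from the protocol. Each one would move an arm's rate by 4.0 points at 25 per arm, or 4.5 at 22. The primary pain analysis, the sample size and the safety reporting are unaffected. It should be corrected, but it does not threaten the trial's main conclusion.

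**What to change.** In section 3.2.2 and in the synopsis, replace *or* with *and* in the BILAG component, so that both conditions are required: no new A, and at most one new B. The component then becomes the per-visit complement of the flare endpoint in 3.2.3. Confirm that the central scoring program applies the same rule.

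Across visits the two may still differ: a flare at Visit 3 and a response at Visit 5 are compatible.

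The cost is one word in two places. No data, visits or additional analyses are needed.

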3.2.3 Safety Endpoints

Safety will be evaluated by describing incidence of treatment-emergent adverse events (TEAEs) from Visit 1 (Day 1) through 6. TEAEs will be identified by monitoring subject-reported AEs, vital signs, medical history, physical exams, blood and urine safety tests, 12-lead electrocardiograms, and the ARCI-M. Analyses on the following specific events are planned.

- 1. Any Grade 3 or higher AE or SAE that, in the opinion of the blinded site investigator, is at least possibly related to study product. Unless noted otherwise, grading is defined by the National Cancer Institute (NCI) Common Terminology Criteria for Adverse Events (CTCAE) system version 4.0.
- 2. QTc prolongation > 500 msec total duration and > 60 msec from Visit 1 (Day 1) QTc interval prior to study drug administration
- 3. Mild/moderate and severe disease flares by SELENA SLEDAI Flare Index
- 4. BILAG 2004 disease flares, defined as one new BILAG A or two new BILAG B scores
- 5. Aspartate aminotransferase (AST) or alanine aminotransferase (ALT) \ge 3 x upper limit of normal and total bilirubin > 1.5 x the upper limit of normal (confirmed on repeat testing)
- 6. Tolerability, assessed by incidence of discontinuation of study product due to TEAEs at least possibly related to study product from Visits 1 (Day 1) through 5 (Day 85)
- 7. Psychotropic activity, assessed using the ARCI-M

3.2.4 Mechanistic Endpoints

- 1. Trends in C-reactive protein levels in the blood over the duration of the treatment period (i.e. Visit 1 (Day 1) through Visit 5 (Day 85)) will be evaluated longitudinally
- 2. Persistence of trends in C-reactive protein levels after stopping treatment will be evaluated at Visit 6 (Day 113)
- 3. Trends in pro-inflammatory cytokine levels over the duration of the treatment period (i.e. Visits 1 (Day 1), 3 (Day 29) and 5(Day 85)) will be evaluated longitudinally using multiple indices:
 - Pro-inflammatory cytokines in serum
 - i. IFN α , IFN γ , IL-6, TNF α , and IL-1 β
 - ii. Expression of other cytokine will be explored
 - Pro-inflammatory cytokines in whole blood with and without in vitro TLR stimulation
 - i. IFN α , IFN γ , IL-6, TNF α , and IL-1 β in supernatant of stimulated and unstimulated whole blood cells
 - Type 1 IFN gene signature in whole blood mRNA

- 4. Persistence of trends in biomarkers of inflammation after stopping treatment will be evaluated at Visit 6 (Day 113)
- 5. Changes in bioactive lipids in plasma from Visit 1 (Day 1) (pre and post dose) to Visit 2 (Day 15) will be evaluated longitudinally using multiple indices:
 - Specialized Pro-resolving lipid Mediators (SPMs), including lipoxin A4
 - Anti-inflammatory eicosanoids
 - Pro-inflammatory eicosanoids
- 6. Changes in plasma concentrations of JBT-101 and its metabolites from Visit 1 (Day 1) (pre and post dose) to Visit 2 (Day 15)

3.2.5 **Exploratory Endpoints**

1. Changes in Fibromyalgia Symptom Scale score, from Visit 1 (Day 1) to Visits 5 (Day 85) and 6 (Day 113)

4 SELECTION OF SUBJECTS

The target population is adults with SLE who have active musculoskeletal disease (arthritis or tendonitis) with significant inflammatory pain, despite treatment with an anti-malarial drug unless intolerant of an anti-malarial drug, and who are on stable doses of prednisone \leq 10 mg daily or equivalent for at least 14 days prior to assessment of 7-day average of maximum daily pain NRS score at Screening and 42 days prior to Visit 1 (Day 1).

Women and minorities will be recruited. Based on the demographics of this disease and the sites that will be used, it is anticipated that approximately 90% of the study population will be women and 60-75% will be African American and Hispanic or Asian. Urban sites will be included, to increase opportunities to enroll minority subjects. Pregnant and lactating women will be excluded from the study because of the unknown effects of JBT-101 on the fetus. Subjects < 18 years of age will be excluded, because there are no toxicology studies in juvenile animals and no safety, tolerability, and efficacy data in adults with SLE.

4.1 Inclusion Criteria

Individuals who meet ALL of the following criteria at Screening are eligible for enrollment:

- 1. Fulfill the updated ACR 1997 Revised Criteria for the Classification of Systemic Lupus Erythematosus [108]
- 2. ≥ 18 and ≤ 70 years of age at the time the Informed Consent Form is signed
- 3. At least 3 months treatment with an anti-malarial drug such as hydroxychloroquine or a history of intolerance, contraindication, or unwillingness to take an anti-malarial drug
- 4. Meets the SELENA SLEDAI definition of arthritis [109] or moderate arthritis or tendonitis that has not improved over the last month (i.e. BILAG B on the updated BILAG 2004 [110])

- 5. Seven-day average of maximum of daily pain NRS scores ≥ 4 out of 10 during screening with continued reporting of pain NRS scores on at least 67% of days between the Screening visit and randomization.
- 6. Overlap with polymyositis, systemic sclerosis, Sjögren's syndrome, or rheumatoid arthritis is allowed, if, in the site investigator's judgment, the predominant clinical features are those of SLE
- 7. Not expected by the site investigator to require a change in potential disease-modifying treatments for SLE from Screening through Visit 6 (Day 113)
- 8. Willing to not start or stop any NSAIDs or potential disease-modifying medications or supplements for SLE from Screening through Visit 6 (Day 113), unless a change is recommended by the site investigator or other treating physicians
- 9. Willing not to use any legal or illegal cannabinoids, including FDA-approved cannabinoids or cannabinoid-mimic drugs, or any illegal substance of abuse from Screening through Visit 6 (Day 113)
- 10. If a woman of child-bearing potential, willing to use one of the highly effective (failure rate < 1% per year) birth control method from Screening through Visit 6 (Day 113) or for 28 ± 3 days after the last dose of study product (See Appendix A: Reproductive Potential and Effective Methods of Contraception)
- 11. Willing to follow instructions, complete study procedures and attend study visits as required by this protocol

